[name]

NCT04011436

Therapeutic Effect of Two Muscle Strengthening Programs in Patients with Patellofemoral Pain Syndrome

**Therapeutic Effect of Two Muscle Strengthening
Programs in Patients with Patellofemoral Pain
Syndrome from Bogota, Colombia.
Experimental Study, Clinical Controlled Trial.**

NCT: 04011436

Date of creation: July 1, 2018.

PROCESSING AND DATA ANALYSIS.

For the classification and verification of the information, the database was refined by recoding and labeling the variables necessary for the analysis, in addition, the variables that required it were converted to alphanumeric format and the review of extreme non-plausible data was performed. For the continuous variables in which two attempts were made as balance and plate a new variable was generated with the average of the measurements and in this way obtain the final result for the analyzes.

Univariate Analysis

The report of absolute and relative frequencies was made; the qualitative variables were presented in proportions and 95% confidence intervals. The normality of the continuous variables was evaluated by scatter plots (histograms, Kernel density and Q-Norm) and the numerical test of Shapiro-Wilk, and according to their distribution they were reported as means and standard deviations, when they had a distribution normal, or on the contrary, as medians and interquartile ranges.

Bivariate Analysis

In the bivariate analysis, a comparison of each of the Kujala test domains was initially performed to assess pain in the baseline, assessing the differences between the intervention groups using the chi-square or Fisher's exact tests. Additionally, the Spearman correlation coefficient was used to evaluate the relationship between two continuous variables, such as the Q angle and the anterior knee pain, evaluating the correlation in a marginal and conditioned way to each of the treatment groups.

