Later, to evaluate if there were differences between the groups of treatment after the intervention on the variables of interest, deltas were generated from the Kujala test, EVA, number of squats, Q angle, balance, physical activity and core strength. with iron and trunk extension, evaluating normality by means of graphic and numerical methods. For the analysis of the differences of medians between the groups, taking into account that the outcomes did not present a normal distribution, and assuming the assumption of independence of the variables, we proceeded to use the non-parametric Mann-Whitney U test. Finally, through the Wilcoxon test, intragroup differences were evaluated for strength, pain and physical activity components.

The hypothesis tests were presented in two tails with an alpha of 0.05 and all the analyzes were executed with the statistical program STATA version 14.0.

BASELINE:

Study population

Therapeutic Effect of Two Muscle Strengthening Programs in Patients with Patellofemoral Pain Syndrome

Table 5 describes the general characteristics of the study population at baseline. There were no significant differences between the two intervention groups (A and B), which means that the randomization was adequate; however, in the total score of the Kujala test there was a difference of 12.5 points between the groups, with a lower score for group B (53.0), which indicates better core strength for these patients. Finally, the sex variable was defined as categorical and the rest of the variables as continuous, for which the medians and their respective interquartile range (IR) are reported, taking into account that the variables did not have a normal distribution.

Table 5: Baseline variables of the study population

Variables	Treatment A (n 20) Medium (RI)	Treatment B (n 20) Medium (RI)	Value p ^a
Sex * (Male, Ref)			
Female	90 (65.7-97.6) *	90.0 (65.7-97.6) *	1,000 ^b
Age	32.5 (25.5-38.0)	29.0 (25.0-36.5)	0,569
Initial weight (Kg)	64.6 (55.3-72.4)	62.7 (52.9-68.5)	0.379
Size (cm)	160 (156.5-167.0)	159.5 (154.0-163.0)	0.423
IMC	25.4 (21.5-27.9)	23.8 (22.3-25.2)	0.456
% of fat	35.4 (28.9-40.4)	35.4 (24.5-38.7)	0,714
% muscle	26.9 (24.5-28.9)	26.2 (24.6-29.0)	0.849
Visceral fat	6 (3.5-7.09)	5 (4.0-6.0)	0.433
IPAQ (minutes)	3003 (1116-4638)	1617 (944-6138)	0,588
Pain	7.5 (5.5-9.0)	7.0 (5.5-8.5)	0.764
Kujala total score	65.5 (42.5-72.5)	53.0 (44.5-71.5)	0,892
Q angle			
Straight	19.0 (15.0-20.0)	18.0 (15.0-20.0)	0,557

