To evaluate the effect of muscle strength on the alignment of the knees and analyze the effect of muscle strength on the unipodal balance, **Table 8** shows the deltas of the medians (changes or differences observed after the intervention) for each of the treatment groups and for each of the variables measured at the beginning and end of the intervention.

In this way, when they include or add exercises for the strengthening of the core, to the traditional treatment of SPF or anterior knee pain, the quality of life measured with the Kujala test in these patients increases, especially by the significant reduction of pain, highlighting for example, that for the total score of the Kujala test, there was a statistically significant difference ($p = 0.025$), with an increase of 5 points for group A (group A = 23.0, group B = 17.0), which indicates that the population of the study group improved their quality of life more after the intervention compared with the people of group B. A similar effect is observed in the increase of the strength of the core musculature for group A, especially in the oblique force evaluated with the side plate, with a difference of 30 seconds for group A, and only five seconds for group B on the left lateral plate, with a statistically significant p value (<0.001).

Therapeutic Effect of Two Muscle Strengthening Programs in Patients with Patellofemoral Pain Syndrome
On the other hand, the differences for the total pain evaluated with EVA were -6 and -4 for group B, with an interquartile range (-10; -4) and (-7; -3) respectively. Although p was not statistically significant, these differences were clinically relevant. For the hip and knee muscle strength, measured with the squat test, there was no statistically significant difference in the median of the deltas between the treatment groups, but there was one in each group, which means that all of them increased strength muscle in hips and knees, as a result of strengthening for these muscle groups.

Table 8: Effect of muscle strengthening on pain, knee alignment, core, hip and knee strength and balance by treatment groups.

Variable	Treatment A			Treatment B			Value p *
	Initial Medium (RI)	Final Medium (RI)	Delta Medium (RI)	Initial Medium (RI)	Final Medium (RI)	Delta Medium (RI)	
Pain (EVA)	7.5 (5.5-9.0)	2 (0-2)	-6 (-10; -4)	7.0 (5.5-8.5)	2.0 (0-4)	-4 (-7; -3)	0.058

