Kujala total test score	65.5 (42.5-72.5)	88.0 (81.0-95.0)	23.0 (16.0-37.0)	53.0 (44.5-71.5)	78.0 (64.0-88.0)	17.0 (8.0-24.0)	0.025
Squats	10.0 (8.0-18.5)	35.0 (30.0-38.0)	20.0 (18.0-25.0)	12.5 (8.5-20.0)	35.0 (29.0-38.0)	20.0 (15.0-24.0)	0.670
IPAQ (minutes)	3003 (1116-4638)	4275 (2587-6522)	1539 (807-2457)	1617 (944-6138)	4598 (2888-7344)	1977 (1191-2815)	0,492
Q angle							
Straight	19.0 (15.0-20.0)	18.0 (15.0-20.0)	0 (-2; 2)	18.0 (15.0-20.0)	18.0 (15.0-20.0)	0 (-2; 2)	0.819
Left	18.0 (15.0-20.0)	18.0 (16.0-20.0)	0 (-2; 2)	18.0 (15.0-20.0)	18.0 (15.0-20.0)	0 (-2; 2)	0.672

Balance with open eyes							
Straight	30.0 818.25- 45.0)	45.0 (45.0- 45.0)	11.5 (0- 25.5)	40.0 (18.25- 45.0)	45.0 (45.0- 45.0)	7.5 (0- 30.0)	0.916
Left	29.5 (15.75- 44.0)	45.0 (45.0- 45.0)	9.5 (0- 21.5)	25.75 (14.5- 45.0)	45.0 (45.0- 45.0)	20.0 (0- 30.0)	0.282
Balance with closed eyes							
Straight	4.5 (3.0- 9.259)	28.5 (21.0- 35.0)	20.0 (14.0- 27.5)	5.25 (3.0- 7.25)	23.5 (16.5- 31.5)	19.0 (9.5- 24.0)	0.671
Left	5.0 (3.0- 8.7)	30.0 (23.5- 38.0)	24.5 (13.0- 30.5)	4.25 (3.5- 7.259)	27.5 (14.0- 34.5)	20.0 (10.5- 30.5)	0.349
Griddle	20.5 (12.0- 32.0)	60.0 (45.0- 70.0)	37.0 (24.0- 48.0)	30.0 (13.5- 33.5)	35.0 (20.0- 60.0)	10.0 (2.0- 15.0)	<0.001
The t. Right	15.0 (10.0- 21.0)	45.0 (38.0- 51.0)	30.0 (19.0- 36.0)	15.0 (9.5- 20.0)	22.0 (16.0- 38.0)	6.0 (2.0- 12.0)	<0.001
The t. Left	12.5 (10.5- 19.0)	45.0 (36.0- 56.0)	30.0 (17.0- 40.0)	18.0 (11.0- 23.0)	21.0 (15.0- 34.0)	5.0 (-2 - 10.0)	<0.001
Trunk extension	13.5 (6.0- 26.5)	61.0 (50.0- 75.0)	49.0 (30.0- 55.0)	13.5 (2.5- 20.0)	30.0 (15.0- 60.0)	15.0 (7.0- 34.0)	0.001

* U of Mann-Whitney for the delta of the measurements between the groups.

He was also interested in this research, to observe the intra-group differences of including hip and knee muscle strengthening exercises (conventional physiotherapeutic treatment) performed in the same way for both intervention groups, as mentioned in the description of the strengthening protocol.

Intragroup differences

Therapeutic Effect of Two Muscle Strengthening Programs in Patients with Patellofemoral Pain Syndrome

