Table 10: Correlation between differences in muscle strength and balance by treatment groups

Therapeutic Effect of Two Muscle Strengthening Programs in Patients with Patellofemoral Pain Syndrome

Variable	Squats	
Balance	Treatment A *	Treatment B *
Right with open eyes	0,558	0.121
Left with open eyes	0,554	0.110
Right with closed eyes	0.390	0.009
Left with closed eyes	0.008	-0.244

* Spearman correlation coefficient.

With the previously stated results, the alternative hypothesis of this study is rejected, which means that adding core exercises to traditional hip and knee muscle strengthening for the treatment of anterior knee pain in patients diagnosed with SPF is more effective in reducing pain and improving the quality of life of these people, they do only hip and knee strengthening exercises.

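### Kujala carries the quality-of-life conclusion, yet its headline difference is printed as 5 points where the SAP's own medians give 6, with no between-arm estimate, confidence interval or number analysed

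*SAP*

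**What the plan says.** The SAP is written in the past tense and includes results.

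- **Test.** Under Bivariate Analysis, changes (deltas) in each outcome are compared between arms: "we proceeded to use the non-parametric Mann-Whitney U test". The footnote to Table 8 confirms this: "U of Mann-Whitney for the delta of the measurements between the groups".
- **Intervals.** Under Univariate Analysis, "the qualitative variables were presented in proportions and 95% confidence intervals". No interval is planned or shown for a between-arm difference in a continuous outcome.
- **Headline.** Under Post-Intervention Results, the size of the Kujala effect, significant at p = 0.025, is described in these words: "with an increase of 5 points for group A (group A = 23.0, group B = 17.0". From this the SAP draws its inference about the arm with core exercises: "which indicates that the population of the study group improved their quality of life more after the intervention".
- **Conclusion.** The closing paragraph after Table 10 says that adding core exercises "is more effective in reducing pain and improving the quality of life of these people".
- **Numbers analysed.** Tables 5 and 6 are headed 20 per arm. Tables 8 and 9, which hold the follow-up results, carry no n.
- **Baseline.** Under Study population, group B's lower Kujala median (53.0 against 65.5) is taken to show a stronger core. The absence of significant baseline differences is taken to show that randomization worked.

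**The concern.** Of the three patient-reported outcomes in Table 8, only Kujala separates the arms (p = 0.025, against 0.058 for pain and 0.492 for IPAQ). The between-group claim on quality of life therefore depends on this one row, and the one figure given for the size of its effect does not follow from the medians beside it.

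The Mann-Whitney test is a valid choice. It yields a p-value, however, and does not estimate a difference of medians, although the SAP introduces it as an analysis of such differences. Without a matching estimate and interval, a reader cannot tell a negligible benefit from a large one. Without the number analysed, a reader cannot tell whether everyone randomized is included.

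The two baseline remarks matter less, but one reverses the direction of the key outcome and the other draws an inference that significance tests cannot support.

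**Working it through.** **1. The headline figure.** Inputs from Table 8, Kujala medians (initial, final, delta): A 65.5, 88.0, 23.0; B 53.0, 78.0, 17.0.

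- Difference in median change: 23.0 − 17.0 = **6.0**
- Difference in final medians: 88.0 − 78.0 = 10.0
- Difference in change of medians: (88.0 − 65.5) − (78.0 − 53.0) = 22.5 − 25.0 = −2.5
- Mixed: 22.5 − 17.0 = 5.5

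The printed 5 is not reproduced by any of these. The medians quoted with it give 6.

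**2. A rough size for the effect.** Inputs: delta quartiles 16.0, 23.0, 37.0 (A) and 8.0, 17.0, 24.0 (B). Assumptions: 20 per arm (not stated for follow-up), SD = IQR/1.349, mean = average of the three quartiles. The SAP calls the data non-normal, so this is only a guide.

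- SD: A (37.0 − 16.0)/1.349 = 15.57; B (24.0 − 8.0)/1.349 = 11.86
- Mean: A 76/3 = 25.33; B 49/3 = 16.33; difference 9.0
- SE = √(15.57²/20 + 11.86²/20) = 4.38
- 95% CI (unequal-variance t, multiplier 2.03): 9.0 ± 8.88 = **0.1 to 17.9**
- With 19 per arm: SE 4.49, 9.0 ± 9.13 = **−0.1 to 18.1**

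As a cross-check, whole-number data were simulated to match the quartiles, with assumed tails and 19 or 20 per arm. Data sets with p between 0.02 and 0.03 gave Hodges-Lehmann shifts of about 8 to 11, with lower limits of 1 to 2 and upper limits of 15 to 20. The reported p of 0.025 is plausible, but it cannot be recomputed without patient data.

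**3. The number analysed.** Count of medians and quartiles ending in .5, both arms:

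| Outcome | Baseline | Final and delta |
|---|---|---|
| Kujala | 5 of 6 | 0 of 12 |
| Pain | 4 of 6 | 0 of 12 |
| Squats | 3 of 6 | 0 of 12 |
| Total | 12 of 18 | 0 of 36 |

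If scores are whole numbers, half-points arise when two neighbouring values are averaged, as happens with n = 20. With an odd n such as 19, the median and (on a common definition) the quartiles are single observed values.

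The pain row points the same way. Group A's delta has a lower quartile of −10. Assume a 0 to 10 scale and n = 20, with the quartile taken between the 5th and 6th values. Both must then be −10, so six patients started at 10 and the baseline upper quartile would be 10. Table 8 gives 9.0. With 19 at follow-up, only five such patients are needed. Among 20 at baseline, the upper quartile is then the average of the 15th and 16th values, and 8 and 10 give 9.0.

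**4. The baseline text.** The gap reproduces: 65.5 − 53.0 = 12.5. Post-Intervention Results treats a rise in Kujala as improvement, so a lower score is worse. The text introducing Table 6 says that the domain results agree with the total score and lists mostly worse answers in B. Core strength is measured separately, by planks and trunk extension. The core-strength reading of B's lower score therefore has the direction reversed and names the wrong construct.

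**The case against.** The strongest reply is that this is incomplete reporting with text slips, and not a faulty analysis. The test is valid, the correct medians stand next to the wrong 5, and the translation is rough. "shows the deltas of the medians (changes or differences observed after the intervention") is loose wording, but the same section also writes "there was no statistically significant difference in the median of the deltas between the treatment groups", and the Table 8 footnote is clear. The core-strength clause may be a misplaced remark, since B's medians were nominally higher on two planks (prone 30.0 against 20.5; left side 18.0 against 12.5). All of this is fair, and it limits the point to the missing estimate, interval and n, plus the text corrections.

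A reader might also infer more than the documents support:

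- **That the effect reverses**, because the change in medians favours B by 2.5. A median of changes need not equal a change in medians, so this is no contradiction.
- **That the arms were unbalanced**, because the baseline medians differ by 12.5. Table 5 gives p = 0.892 and nearly the same quartiles (42.5–72.5 against 44.5–71.5). Table 6 is mixed.
- **That an interval touching zero contradicts p = 0.025.** The interval above is a normal-theory approximation for a mean difference, and the p-value comes from a rank test. For the same reason, its standard error should not be placed around the difference of medians, 6.
- **That patients dropped out.** The half-point pattern and the pain quartile rest on assumptions about the scale, whole-number scores and the quartile definition. They justify a question to the sponsor and prove nothing.

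**Conclusion.** The point stands as a reporting defect in the outcome that matters most. The stated difference should be 6 points and not 5, and 6 is itself only a description, not the shift that the Mann-Whitney test addresses. The benefit has no estimate, interval or denominator. Under the assumptions stated, the mean difference is about 9 points, with an interval from about zero to about 18. The lower end is too close to zero for a reader to judge the benefit from the p-value alone. Whether fewer than 20 per arm were analysed is an open question. The two baseline inferences are unsupported by the SAP's own text and tables. None of this shows that the Kujala result is biased, inflated or reversed.

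**What to change.** Keep the Mann-Whitney test and make these changes:

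1. Under Post-Intervention Results, change 5 points to 6 points and label it the difference in median changes.
2. Report the Hodges-Lehmann shift in Kujala change with its 95% CI. Suggested wording: *Median change 23.0 in A (n = __) and 17.0 in B (n = __), difference in median changes 6 points; Hodges-Lehmann shift __ (95% CI __ to __); Mann-Whitney p = 0.025.*
3. State the number analysed per arm in Table 8 and account for any patient missing at follow-up.
4. Under Study population, delete the clause inferring adequate randomization and the clause linking B's lower Kujala to core strength. If a reading is kept, say only that B's median was lower (lower is worse) and that the distributions did not differ detectably (p = 0.892).

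Optionally, add a baseline-adjusted Kujala comparison (ANCOVA of final score on baseline, with a robust or bootstrap interval), labelled post hoc and supportive. The reason is precision only, and the price is the assumption of a common slope in both arms.

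The cost is small: items 1 and 4 are edits, items 2 and 3 use data already held, and the ANCOVA is one extra model.

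### The conclusion claims superiority of program A on pain (p = 0.058) and quality of life (Kujala p = 0.025, one of 14 unadjusted tests), with no primary outcome or multiplicity strategy in the available text

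*SAP*

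**What the plan says.** The SAP's Bivariate Analysis section sets out the between-group comparison: "deltas were generated from the Kujala test, EVA, number of squats, Q angle, balance, physical activity and core strength". These seven domains are listed without ranking. For each change score, "we proceeded to use the non-parametric Mann-Whitney U test". The error rate is set test by test: "The hypothesis tests were presented in two tails with an alpha of 0.05". The available text gives no primary outcome, testing order or adjustment.

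Table 8 (Post-Intervention Results) carries the comparisons, and its footnote describes the p-value column as "U of Mann-Whitney for the delta of the measurements between the groups". The text introducing the table reports that "for the total score of the Kujala test, there was a statistically significant difference", with p = 0.025. On the visual analogue pain score (EVA) it says: "Although p was not statistically significant, these differences were clinically relevant".

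The closing paragraph, after Table 10, concludes that adding core exercises to hip and knee strengthening "is more effective in reducing pain and improving the quality of life of these people" than hip and knee strengthening alone.

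**The concern.** The closing paragraph is a confirmatory verdict on two outcomes, but nothing in the available text sets those two apart from the other rows of Table 8. With 14 comparisons each read against 0.05, a p-value of 0.025 is weaker evidence than it looks in isolation. The pain half has a more basic problem: its between-group test is not significant before any adjustment, and the SAP says so itself.

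At stake is the trial's efficacy statement. As written, a reader takes away two established patient-reported benefits. The table's strongest between-group evidence concerns core endurance, which the closing paragraph does not mention as a finding.

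**Working it through.** **Inputs (SAP, Table 8, between-group p-values)**

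| Domain | Tests | p-values |
|---|---|---|
| Core strength (prone plank, side plank right and left, trunk extension) | 4 | <0.001, <0.001, <0.001, 0.001 |
| Kujala total | 1 | 0.025 |
| Pain (EVA) | 1 | 0.058 |
| Balance (eyes open right and left; eyes closed right and left) | 4 | 0.916, 0.282; 0.671, 0.349 |
| Physical activity (IPAQ) | 1 | 0.492 |
| Squats | 1 | 0.670 |
| Q angle (right and left) | 2 | 0.819, 0.672 |

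Total: 4 + 1 + 1 + 4 + 1 + 1 + 2 = 14. Kujala is the fifth smallest and pain the sixth. Entering <0.001 as 0.001 or as 0.0001 does not change the Kujala results.

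**1. The plan's own figure.** A Mann-Whitney p-value cannot be rebuilt from medians and quartiles, so this is a plausibility check only. It assumes 20 per arm, mean = (lower quartile + median + upper quartile)/3 and SD = interquartile range/1.35.
- A: mean (16 + 23 + 37)/3 = 25.33; SD 21/1.35 = 15.56.
- B: mean (8 + 17 + 24)/3 = 16.33; SD 16/1.35 = 11.85.
- t = 9.00 / √(15.56²/20 + 11.85²/20) = 2.06, p ≈ 0.046.

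This is the same order as 0.025. The printed value is used below.

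**2. Scale of the problem.** If all 14 null hypotheses were true and the tests independent, the chance of at least one p below 0.05 would be 1 − 0.95^14 = 0.51. The rows are correlated (paired sides, related plank tests), so this is an upper-end illustration.

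**3. Family of 14 tests**
- Bonferroni, Kujala: 14 × 0.025 = 0.35.
- Holm, Kujala (rank 5, multiplier 14 − 5 + 1 = 10): 10 × 0.025 = 0.25.
- Benjamini-Hochberg, Kujala: 0.025 × 14/5 = 0.07.
- Holm, pain (multiplier 9): 9 × 0.058 = 0.52.
- Core endurance: the largest Bonferroni value is 14 × 0.001 = 0.014, so all four results stay below 0.05.

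**4. Family of seven domains.** This takes the smallest p-value in each domain and makes no allowance for choosing within a domain. Kujala is second, behind core strength.
- Holm (multiplier 7 − 2 + 1 = 6): 6 × 0.025 = 0.15.
- Benjamini-Hochberg: 0.025 × 7/2 = 0.0875.

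**5. Family of two (pain and Kujala)**
- Bonferroni or Holm: 2 × 0.025 = 0.050.
- Rounding of the printed value decides the side: 2 × 0.0245 = 0.049; 2 × 0.0255 = 0.051.

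**6. Kujala as sole pre-specified primary outcome, or first in a fixed sequence.** No correction applies; 0.025 < 0.05.

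**7. Pain.** 0.058 > 0.05 with no adjustment, so no choice of family rescues it.

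**The case against.** The strongest reply is that the relevant family may not be 14. The opening part of the protocol is not in the available text, and what remains of the protocol describes only the intervention. The closing paragraph refers to a study hypothesis that is not shown, and the sentence after that reference concerns pain and quality of life. If that hypothesis was fixed in advance, the family could be two outcomes, or Kujala could be primary. This stands. A reader might infer that no primary outcome was ever specified, or that pain and Kujala were selected after the results were seen; the documents establish neither.

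A reader might also infer that Kujala fails every standard correction. It does not. It is at the limit in a family of two, where Šidák gives 1 − 0.975² = 0.049, and it needs no correction as a sole primary outcome. Over the 14 tests, Benjamini-Hochberg misses modestly at 0.07, and the less usual two-stage adaptive version lands at 0.050. Nor is 51% this trial's error rate: it assumes independence and 14 true nulls, while four core results survive adjustment.

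Finally, Table 8 prints every p-value, so nothing is hidden, and exploratory results need no formal correction. Both points are fair. But the closing paragraph is not worded as exploratory. On pain, describing the difference as clinically relevant does not turn p = 0.058 into demonstrated superiority. The within-group reductions in Table 9 (p < 0.001 in both arms) show that both arms improved, not that one improved more.

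**Conclusion.** The point holds, within limits. The between-group pain claim is unsupported at the SAP's own alpha, and multiplicity is not the reason. The quality-of-life claim depends on one unadjusted p-value of 0.025 whose standing turns on a family the available text does not define: not significant over 14 tests or seven domains, on the boundary for two outcomes, significant if Kujala was the pre-specified primary outcome. Core endurance is the between-group difference that does not depend on that choice.

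This takes the printed p-values as correct. It says nothing against a true Kujala or pain effect: a difference not established after correction is not evidence of no effect.

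**What to change.** - Reword the closing paragraph so that it does not claim a between-group pain benefit and reports core endurance as the difference robust to multiplicity. The same sentence says the alternative hypothesis is rejected while asserting superiority; that needs resolving too.
- If a primary outcome was fixed before the data were seen, cite where it is documented and base the quality-of-life statement on it.
- If not, add Holm-adjusted p-values to Table 8 and describe the Kujala difference as exploratory and not established after correction. Holm over all 14 rows is one defensible family among several, so state the family used. Choosing a primary outcome or a two-outcome family now would not restore error control.
- While editing the Kujala sentence, reconcile the stated 5-point advantage with the medians beside it (23.0 − 17.0 = 6.0).

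The cost is at most one added table column and a few reworded sentences, with no new data. The downside is a weaker quality-of-life claim.

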## INTERVENTION PROTOCOL

From the following scheme (Scheme 3), each training session of the muscle strengthening program was structured for each of the intervention groups, which was based on the principles of training and the Earl and Hoch protocol described in the theoretical framework.

*Scheme 3: A y B Strengthening Program*

After the adjustments described in the pilot test, the strengthening program was applied to the forty patients who were previously randomized to the intervention protocols for groups A and B.

Each of the exercise sessions lasted approximately 45 to 60 minutes, of which, the first 8 to 10 minutes were dedicated to the initial warm-up exercises, the same for program A and B, which gave way to the phase central to the session, that is to say the strengthening exercises: group B took about five minutes less to complete it, because they performed an exercise less than group A in each of the three phases set out in the program; This phase of strengthening lasted approximately 20 to 30 minutes of the total session.

Each session was divided into four parts, of which the second part (central strengthening phase) included between 24 and 28 exercises in total, group A and B respectively. In addition to this, the anatomical conditioning phase was carried out in two weeks, in which 5 to 6 strengthening exercises were prescribed depending on the treatment group, but for both groups the volume was two sets of 10 repetitions, with approximately 30 seconds rest between sets and between exercises, with an execution speed of 1/1 (concentric / eccentric contraction ratio) that allowed patients to adapt to adequate movement control and therefore, joint protection.

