To determine the influence of muscle length (quadriceps, hamstrings, of tensioner of the fascia lata and gastrocnemius) on the alignment of the patella, in **Table 7**, the influence of muscle length on patellar alignment is observed, highlighting that the Right angle Q for people with a positive Ober

Therapeutic Effect of Two Muscle Strengthening Programs in Patients with Patellofemoral Pain Syndrome test (which evaluates the muscle length of tensioner of the fascia lata), obtained an average of 17.26 while for the left Q angle was 18.07 with one and one standard deviation of 3.88 and 4.11 respectively, indicating that those people with decreased muscle length, that is, a positive Ober test, had a higher Q angle compared to those who obtained a negative test. In the same way, a similar effect is observed in the 90-90 test which evaluates the muscle length of the hamstrings, because when the test is negative, that is, there is less muscle retraction, the angle Q is smaller, indicating lesser mal patellofemoral alignment.

Table 7: Influence of muscle length on the alignment of the patella

[figure not shown]
Test	Q angle	
	Straight Half of)	Left Half of)
Ober		
Positive	17.26 (3.88)	18.07 (4.11)
Negative	16.28 (3.51)	16.96 (3.82)
90-90		
Positive	17,02 (3,81)	17,32 (3.90)
Negative	15.0 (0.00)	-
ELY ^a	0.30	0.12
Lunge ^{to}	0.20	-0.08

a: Spearman correlation coefficient

Now, **Figure 5**, highlights the relationship between the muscle length of the quadriceps and the gastrocnemius, measured in degrees and centimeters respectively, and the bilateral Q angle of knees, indicating that there is a positive correlation for both knees in the Ely test, and for the right knee in the Lunge test, this correlation being slight, which suggests that when the muscle length is greater, the angle Q is smaller, whereas for the left knee in the Lunge test, the correlation was negative (-0.08), classified as very mild.

Figure 5: Relationship of muscle length using the Ely and Lunge tests on the bilateral Q angle of the knees.

Therapeutic Effect of Two Muscle Strengthening Programs in Patients with Patellofemoral Pain Syndrome

Source: Author.

Post-Intervention Results

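### Table 7 of the SAP summarises a variable declared non-normal by mean (SD), against the plan's own rule, and states a direction for Q angle by Ober result that its figures do not support

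*SAP*

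**What the plan says.** The SAP's Univariate Analysis section sets one reporting rule for continuous variables: "according to their distribution they were reported as means and standard deviations, when they had a distribution normal". Any other continuous variable is to be given by its median and interquartile range.

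The baseline section (Study population) applies it. It treats every variable except sex as continuous and gives medians with interquartile ranges, "taking into account that the variables did not have a normal distribution". Q angle is one of these variables. Table 5 gives the right Q angle as 19.0 (15.0 to 20.0) in arm A and 18.0 (15.0 to 20.0) in arm B, and the left as 18.0 (15.0 to 20.0) in both arms. Table 8 also uses medians for Q angle.

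Angle Q and Muscular Length (Table 7), still among the baseline results, changes the summary. Ober-positive patients "obtained an average of 17.26 while for the left Q angle was 18.07", with a "standard deviation of 3.88 and 4.11 respectively". The text then states that patients with the shorter muscle have the larger Q angle, and describes a similar effect for the 90-90 test. It gives no reason for using means, and no cell counts, test or interval.

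**The concern.** Two things are wrong, and they compound each other. Table 7 departs without explanation from the rule that the plan sets and follows elsewhere for the same variable. The section also sets out to show the influence of muscle length on patellar alignment and reaches a directional statement from two differences in means, with nothing to show how precise they are. A reader cannot tell whether a difference of about one degree, against SDs of 3.5 to 4.1 degrees, is more than chance. If it is not, a claim about muscle length and alignment is being reported that the data do not carry.

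**Working it through.** **Inputs.** The sample size is 40: the Protocol refers to "the forty patients who were previously randomized", and Table 5 has 20 per arm. Table 7 gives these values, mean (SD):

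| Cell | Right | Left |
|---|---|---|
| Ober positive | 17.26 (3.88) | 18.07 (4.11) |
| Ober negative | 16.28 (3.51) | 16.96 (3.82) |
| 90-90 positive | 17.02 (3.81) | 17.32 (3.90) |
| 90-90 negative | 15.0 (0.00) | none |

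The column heading is garbled, but the text names an average and a standard deviation, so these are means and SDs.

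**Step 1: cell counts.** Table 7 prints none, but the Ober split and the 90-90 split must give the same whole-sample total for each knee. With 40 patients per knee and whole-degree readings, and allowing two-decimal rounding or truncation, one solution per knee reproduces the printed means. Half-degree readings give the same solution.

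- Right: 449/26 = 17.269 (printed 17.26) and 228/14 = 16.286 (printed 16.28), total 677. With 2 patients negative on 90-90, (677 - 2 × 15)/38 = 17.026 (printed 17.02).
- Left: 235/13 = 18.077 (printed 18.07) and 458/27 = 16.963 (printed 16.96), total 693. With none negative on 90-90, 693/40 = 17.325 (printed 17.32).

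**Step 2: check against the SDs, which were not used in step 1.** The whole-sample SD from any split is √{[Σ(nᵢ - 1)sᵢ² + Σnᵢ(mᵢ - M)²]/39}, where M is the whole-sample mean.

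- Right: 3.74 from the Ober split (26 and 14) and 3.74 from the 90-90 split (38 and 2).
- Left: 3.90 from the Ober split (13 and 27), against 3.90 printed for the whole left sample.

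The inferred counts agree with the SDs on both sides.

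**Step 3: Ober difference in means.** The pooled variance is s² = [(n₁ - 1)s₁² + (n₂ - 1)s₂²]/38, the standard error is s√(1/n₁ + 1/n₂), and the 95% interval uses t = 2.024 on 38 degrees of freedom.

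- Right: difference 17.26 - 16.28 = 0.98; s² = (25 × 3.88² + 13 × 3.51²)/38 = 14.12; s = 3.76; SE = 3.76 × √(1/26 + 1/14) = 1.246. The 95% CI is 0.98 ± 2.52, or -1.54 to 3.50; p=0.44.
- Left: difference 18.07 - 16.96 = 1.11; s² = (12 × 4.11² + 26 × 3.82²)/38 = 15.32; s = 3.91; SE = 3.91 × √(1/13 + 1/27) = 1.321. The 95% CI is 1.11 ± 2.67, or -1.56 to 3.78; p=0.41.

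**Step 4: dependence on the inferred counts.** Over Ober-positive counts from 5 to 35 of 40, using the printed means and SDs, p stays between 0.38 and 0.60 across the two knees. The finding does not hang on the exact split.

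**Step 5: the 90-90 test.** The right-side contrast is 17.02 - 15.0 = 2.02 degrees, but the negative group is about 2 patients, with a printed SD of 0.00. The left has no negative group, so no contrast exists there.

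**The case against.** The strongest case on the other side is that this is an exploratory baseline description. It gives no p-value and makes no claim of significance. The mean-or-median rule sits under Univariate Analysis, whereas Table 7 is a subgroup comparison. The non-normality statement is a blanket one about Table 5, not a result for Q angle within Ober groups. No document prescribes a Mann-Whitney test or a Hodges-Lehmann estimate for this table. The muscle-length discussion also draws on the Ely and Lunge correlations, which are rank-based already.

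Much of this stands, and it limits the weight of the point. It does not remove it. The plan has no other rule for summarising continuous variables, and Table 7 gives no reason for leaving it. The sentence about Ober is literally true of the sample means, but the section offers it as evidence of influence. The lack of n, test and interval would matter equally had medians been used.

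Three stronger readings are tempting, and the documents do not support them.

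- *Medians would remove or reverse the Ober difference.* No median by Ober result is printed and no patient-level data are given. The direction and size of a median difference are unknown.
- *The gap between mean and median discredits the one-degree difference.* The whole-sample right mean, 677/40 = 16.925, lies 1.08 and 2.08 degrees below the arm medians of 18.0 and 19.0. This points to skew, but skew shared by the Ober-positive and Ober-negative groups largely cancels in their difference. The Ober-positive mean of 17.26 is itself only 0.74 below arm B's median.
- *The trial's result is affected.* The between-arm Q angle comparisons in Table 8 use medians of change (p=0.819 right, 0.672 left) and do not depend on Table 7.

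**Conclusion.** The point holds as a minor one. The departure from the plan's rule is plain in the text and needs no calculation. The directional statement about Ober is not supported on either knee: the printed means give intervals that run from about 1.5 degrees below zero to more than 3.5 above, and no other summary by Ober result is reported that could support it. Intervals this wide do not show that muscle length and Q angle are unrelated; they show that the table cannot say.

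The intervals assume 40 patients measured on each knee and whole-degree (or half-degree) readings. They come from a t comparison of means for a variable the SAP calls non-normal, so they indicate scale and do not replace the rank-based analysis. The figure of 2 patients negative on the right 90-90 test rests on the same assumptions.

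**What to change.** In Table 7, report n and median (IQR) of Q angle by Ober and by 90-90 result, separately for each knee. If means are kept, state why. For Ober, add a Mann-Whitney comparison with a Hodges-Lehmann difference and 95% CI. This goes beyond what the SAP prescribes for the table, but is in line with its use of rank methods elsewhere. For 90-90, describe only.

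Reword the text of Angle Q and Muscular Length as descriptive for each knee. Where the interval includes zero, say that no difference was demonstrated. State that the 90-90 negative group is too small on the right, and absent on the left, to support a comparison.

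The cost is one table re-run on existing baseline data and a few sentences of text. No new data are needed and no between-arm result changes.
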